## 5.4 QUALITY OF LIFE

Among the 14 items of the OHIP-14 questionnaire, only three showed significant differences between groups. Regarding mouth opening, 31% of participants in Group A still reported difficulty opening the mouth on postoperative day 7, compared with 23.5% in Group B. Concerning sleep disturbances, Group A showed an approximate 40% reduction in complaints between postoperative days 2 and 7, whereas Group B demonstrated a reduction of approximately 66.6%.

When participants were asked which intervention resulted in greater postoperative improvement, all patients who underwent the control protocol in the first surgery (100%) preferred the cryotherapy intervention. Among those who received cryotherapy during the first procedure, 83% also indicated preference for the cryotherapy side.

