## ABSTRACT

Third molar extraction is a common oral surgical procedure often associated with postoperative pain, edema, and functional limitation. Effective postoperative management plays a key role in minimizing morbidity and promoting patient comfort. Strategies such as cryotherapy may contribute to improved recovery and quality of life after surgery. **Objective:** to investigate the effects of cryotherapy on postoperative outcomes (pain intensity, edema, trismus and quality of life) following mandibular third molar extraction. **Materials and Methods:** This study was designed as a randomized split-mouth clinical trial. The sample consisted of 17 patients (34 mandibular third molars with equivalent levels of impaction) who underwent bilateral surgical extraction. The surgical sites were allocated into two groups according to postoperative care: Group A (control side—without cryotherapy) and Group B (test side—with postoperative cryotherapy using ice packs). All intraoperative and postoperative procedures, instructions, and medications were identical for both groups. Patients were evaluated for pain intensity, trismus severity, presence of edema, and quality of life for up to seven days postoperatively (D7). The evaluator was aware of the postoperative intervention applied. Repeated-measures ANOVA was used to analyze each outcome variable, and associations between continuous variables were assessed using Pearson's correlation test. Statistical significance was set at 5% ( $P < 0.05$ ). **Results:** Overall, postoperative pain intensity was lower in patients who received cryotherapy. Group A reported significantly higher pain intensity on postoperative days 1 and 3. No signs of trismus were observed in Group B at the end of the follow-up period, whereas Group A presented restricted mouth opening at D7. Both groups exhibited edema on postoperative day 2 (D2); however, complete regression of edema by D7 was observed only in Group B. Additionally, a significant association between pain intensity and trismus severity was identified in Group A at D7. Quality-of-life assessment revealed significant differences in three questionnaire items favoring Group B, including greater perceived improvement, better mouth opening, and reduced difficulty sleeping. **Conclusion:** The findings suggest that postoperative cryotherapy is effective in reducing pain intensity and trismus following mandibular third molar extraction. Moreover, this physical therapy modality appears to enhance pain tolerance and patients' self-perceived healing.

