## 4.7 STUDY VARIABLES

The outcome variables of this study were postoperative pain, trismus, local edema, and changes in quality of life following mandibular third molar extraction. Postoperative assessments were performed by the research team, consisting of two calibrated surgeons and one supervising professor, on postoperative days 0 (day of surgery), 2, and 7. The following evaluation protocols were applied:

a) Pain assessment: postoperative pain was assessed using a visual analog scale (VAS– APPENDIX C) ranging from 0 to 10, in which 0 represented no pain, 1–3 mild pain, 3.1–6 moderate pain, and 6.1–10 severe pain. Patients completed the scale at home daily until postoperative day 7.

b) Trismus assessment: trismus was evaluated by measuring maximum mouth opening with the patient seated and the tragus–ala plane parallel to the ground. Patients were instructed to open their mouths three consecutive times, and the mean value was recorded. Measurements were obtained as the interincisal distance in millimeters using a measuring tape. In the absence of maxillary or mandibular incisors, the occlusal edges were used as reference points. Measurements were recorded on postoperative days 0, 2, and 7.

c) Edema assessment: facial edema was measured using the method described by Gabka and Matsumura. Three linear facial measurements were obtained in millimeters with a measuring tape: tragus to pogonion, tragus to oral commissure, and lateral canthus to mandibular angle. The mean of these three measurements was calculated to quantify edema. This assessment was performed preoperatively and on postoperative days 2 and 7.

d) Quality of life assessment: quality of life was evaluated using a questionnaire adapted from the OHIP-14 (APPENDIX D), consisting of 14 dichotomous (yes/no) questions addressing daily functional limitations. The questionnaire included items related to chewing and swallowing ability, dietary changes, alterations in taste, mouth opening, voice changes, speech intelligibility, facial appearance, sleep disturbances, and ability to perform work-related activities. The questionnaire was provided to participants on the day of surgery and completed on postoperative days 0, 2, and 7. At the conclusion of the evaluation period following the second intervention, participants also answered the question: “Which intervention did you perceive as resulting in greater postoperative improvement?”

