#### 4.8 STATISTICAL ANALYSIS

Data normality was assessed using the Kolmogorov–Smirnov test. Parametric analyses were applied to compare groups (control side vs. test side) and postoperative time points (from day 0 to day 7). Continuous variables, including pain intensity (VAS scores), maximum mouth opening (mm), and facial edema (mm), were expressed as means  $\pm$  standard deviation (SD).

A two-way repeated-measures analysis of variance (ANOVA), followed by Fisher's least significant difference (LSD) post hoc test, was used to evaluate the main effects of time and treatment, as well as their interaction, for pain intensity, trismus, and edema. Pain reports were also qualitatively analyzed based on the frequency distribution of pain categories (no pain, mild pain, moderate pain, and severe pain) for both groups.

Associations between pain intensity and trismus or edema were assessed using Pearson's correlation coefficient. Trismus and edema were additionally evaluated using the formulas (Baseline – Postoperative) and (Postoperative – Baseline), respectively. Qualitative data related to quality of life were presented as percentages.

All statistical analyses were performed using SPSS software (version 20.0; IBM Corp., Armonk, NY, USA). Statistical significance was set at  $P < 0.05$ .

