**APPENDIX D – OHIP QUESTIONNAIRE (ORAL HEALTH IMPACT PROFILE)**

	Pre-op	Second day post-op	Seventh day post-op
Did you have difficulty chewing?			
Did you have difficulty swallowing?			
Did you avoid certain foods?			
Have you lost your sense of taste in certain foods?			
Can you open your mouth normally?			
Are you able to taste the food normally?			
Have you noticed any change in your voice?			
Did you have any difficulty speaking?			
Did other people have any difficulty understanding you?			
Has your appearance changed?			
Do you look unusual?			
Are you having trouble sleeping?			
Do you wake up during the night?			
Are you having difficulty performing daily tasks?

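### The claim that three of 14 quality-of-life items differed significantly counts a question outside the 14, and no reported test supports the word significant

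*Combined protocol and SAP*

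**What the plan says.** Section 4.7(d) describes a questionnaire adapted from the OHIP-14, "consisting of 14 dichotomous (yes/no) questions addressing daily functional limitations", completed on days 0, 2 and 7. It then adds that, at the end of the evaluation period "following the second intervention, participants also answered the question" of which intervention had given the greater improvement.

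For the analysis, section 4.8 says: "Qualitative data related to quality of life were presented as percentages". The repeated-measures ANOVA in that section covers pain, trismus and edema only. No test for yes/no items, total score or multiplicity rule is given for quality of life.

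Section 5.4 reports: "Among the 14 items of the OHIP-14 questionnaire, only three showed significant differences between groups". The Abstract reports "significant differences in three questionnaire items favoring Group B, including greater perceived improvement, better mouth opening, and reduced difficulty sleeping". The Discussion (section 6) lists the same three results but calls them noteworthy differences in percentages, not significant ones. It also uses the mouth-opening answers to corroborate the trismus finding.

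**The concern.** Quality of life is one of the four outcomes in the general objective. A reader of section 5.4 or the Abstract would take it that three of 14 questionnaire items passed a test at the 5% level. Two things stand against that.

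- **The count.** One of the three is not a questionnaire item. It is a single choice between sides, so it has no Group A value and Group B value to compare in the way an item does.
- **The word significant.** The plan contains no analysis that could produce it for yes/no items, and the results give no p-value for any item.

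The quality-of-life claim would therefore rest on a wrong numerator and an undocumented test, and part of it is carried into the Discussion as support for a different outcome.

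**Working it through.** **1. Reproducing the plan's figure (3 of 14).** Appendix D lists, in order: chewing, swallowing, avoiding foods, lost taste, mouth opening, normal taste, voice, speaking, being understood, changed appearance, unusual look, trouble sleeping, waking at night, daily tasks. That is 14, and none asks about improvement or preference. Matched to the Abstract's three:

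| Named in the Abstract | In Appendix D? |
|---|---|
| Perceived improvement | No; the separate question in section 4.7(d) |
| Mouth opening | Yes |
| Difficulty sleeping | Yes |

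The figure is not reproduced. At most 2 of 14 items are involved.

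**2. Mouth opening, day 7.** Section 5.4 gives 31% (Group A) and 23.5% (Group B), with 17 patients analysed (section 4.4).
- 4/17 = 23.5%, which matches Group B.
- 5/17 = 29.4% and 5/16 = 31.25%. The reported 31% fits 5/16, meaning one missing answer. Both are carried forward.

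The data are paired, so the exact McNemar test applies: with b and c discordant pairs in the two directions, p is the two-sided binomial probability of a b:c split at 0.5.
- 5/17 vs 4/17: b − c = 1. The most favourable pairing is 1:0, with p = 1.00.
- 5/16 vs 4/17: if the patient missing from Group A is one of the four in Group B, the complete pairs show 5 vs 3. The most favourable pairing is 2:0, with p = 2 × 0.5² = 0.50.
- Other tests agree. Uncorrected McNemar gives p of at least 0.157 (2:0), Fisher 0.71 to 1.00, and chi-square 0.62 to 0.70.

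With no discordant pair in the other direction, exact McNemar first falls below 0.05 at 6:0 (2 × 0.5⁶ = 0.031). The reported percentages allow a net difference of one or two.

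**3. Sleep.** Section 5.4 gives only reductions from day 2 to day 7: about 40% in Group A and about 66.6% in Group B. Counts that fit exactly include 5→3, 10→6 or 15→9 in Group A, and 3→1, 6→2, 9→3, 12→4 or 15→5 in Group B. Across these, the day-7 exact McNemar p in its most favourable pairing runs from 1.00 (for example 3 vs 3) to 0.008 (9 vs 1, so 8:0). The between-side result cannot be recovered. Appendix D also has two sleep items, and section 5.4 does not say which one is meant.

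**4. Preference.** The Discussion gives 11 of 11 for patients who had the control side first. Section 5.4 gives 83% of the remainder: 17 − 11 = 6, and 5/6 = 83%. The total is 11 + 5 = 16 of 17. Two-sided sign test: 2 × (1 + 17)/2¹⁷ = 36/131072 = 0.0003.

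**5. Chance findings, as a sensitivity check.** The number of item tests done is not stated, so 14 (one visit) and 28 (days 2 and 7) are assumptions, as is independence at 0.05 per test. P(≥2) = 1 − 0.95ᵐ − m × 0.05 × 0.95ᵐ⁻¹.
- m = 14: expected 0.70; P(≥2) = 1 − 0.488 − 0.359 = 0.15.
- m = 28: expected 1.40; P(≥2) = 1 − 0.238 − 0.350 = 0.41.
- With an assumed inter-item correlation of up to 0.5, P(≥2) is 0.15 to 0.16 for 14 tests and 0.27 to 0.41 for 28.

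**The case against.** **Preference belongs to the quality-of-life outcome.** Section 4.7(d) places the question under that assessment. Its result, 16 of 17, is a legitimate within-patient comparison and is stronger than either item. This stands: the result should be kept. What fails is counting it among the 14. It is also an unblinded judgement.

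**The conclusions do not depend on the count.** Neither the Abstract's conclusion nor section 7 cites three of 14, and both speak of patients' perceived recovery, which the preference question addresses. This limits the damage. But the count appears in both the Abstract and section 5.4, and the Discussion does lean on the mouth-opening item.

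**Stronger readings a reader might infer.**
- *The result is about what chance would give.* The documents do not support this. With 14 tests, two or more false positives have probability 0.15; only the assumed 28 gives 0.41. No item test is documented, so neither is an established error rate.
- *The items were picked after the data were seen.* The documents do not say when they were chosen. Section 5.4 says only three differed, which implicitly reports the rest as not different. What is missing is their figures.
- *The reversed wording of some items caused an error.* The item "Can you open your mouth normally" runs opposite to most others, but section 5.4 reports it as difficulty, so it was evidently read in the right direction. Direction matters only if a total is formed.

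**Conclusion.** The concern holds in this form: the reported three of 14 is wrong as written, and *significant* is unsupported for the items that remain. That at most two of the 14 are involved rests on the documents' text alone. That mouth opening is not significant rests on reading 31% as 5/16 or 5/17 and 23.5% as 4/17; under either, exact McNemar p is at least 0.50. Sleep is unverifiable, which is not the same as negative.

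A reader might go on to substitute two of the 14 items as the significant count. That would keep a claim the mouth-opening figures contradict. Nor does any of this show that cryotherapy had no effect on quality of life: the preference result is strong, though unblinded, and no overall estimate across the 14 items was planned or reported.

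**What to change.** 1. In section 5.4 and the Abstract, remove the statement that three questionnaire items differed significantly. Say that mouth opening and sleep showed descriptive percentage differences favouring Group B, with no demonstrated significance for mouth opening.
2. In the Discussion, remove the use of the mouth-opening item as corroboration of the trismus result.
3. Report the preference question on its own, as an unblinded within-patient preference: 11/11 control first, 5/6 cryotherapy first, 16 of 17 overall.
4. Tabulate counts and denominators for all 14 items by side and visit. If any item is to be called significant, give its exact McNemar p-value with a multiplicity adjustment, and state in section 4.8 the test and the number of comparisons.
5. Optionally, add a within-patient limitation count per side and visit (0 to 14, with the normal-opening and normal-taste items reversed), compared at days 2 and 7 with a 95% CI. Label it post hoc, since results are known, and note that taste, appearance and sleep each have two items and so count twice.

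The cost is a recount of existing questionnaires and text edits, with no new data. The quality-of-life statement becomes less favourable, but the preference result is kept.

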## 6 DISCUSSION

Cryotherapy was effective in reducing both the intensity and duration of postoperative pain episodes, as well as shortening the period of mouth opening limitation. Additionally, its use in the postoperative period resulted in a reduced need for rescue medication and a greater patient-perceived improvement over time. These findings support the consolidation of a cryotherapy protocol, contributing to a more predictable postoperative course and improving the management of postoperative complications.

As shown in Table 1, differences in mean pain scores during the first 72 postoperative hours (from day 0 to the end of day 2) appear to be related to the lack of consolidation of the inflammatory response under pharmacological analgesia alone. Pain modulation was only stabilized after postoperative day 3 in both groups, as also reported by Sukegawa et al. However, cryotherapy demonstrated a

beneficial synergistic effect when combined with analgesic medication, resulting in lower pain scores during this critical period. In contrast, analgesic therapy alone was insufficient to adequately control pain in the control group, which exhibited two distinct peaks in pain intensity at 24 and 72 hours postoperatively.

The benefit of cryotherapy for the test group was particularly evident between postoperative days 2 (the last day of analgesic medication) and 3 (the first day without medication). During this transition, pain levels increased in the control group and remained consistently higher than those observed in Group B, even during the consolidation phase of the inflammatory response. These findings suggest that the greater differences in pain intensity are directly associated with the absence of cryotherapy in the control group, despite the use of analgesics.

Pain severity distribution over the seven postoperative days further reinforced these findings (Graphics 1 and 2). Proportionally, extractions performed without cryotherapy were associated with a significantly higher likelihood of moderate-to-severe pain. From a clinical perspective, the absence of cryotherapy increased the probability of requiring rescue medication. This observation is particularly relevant for patients with systemic diseases who already require complex pharmacological regimens, increasing the risk of drug interactions, as well as for individuals susceptible to medication dependence, for whom minimizing drug exposure is essential.

A strong association was also observed between higher pain intensity reports and increased requests for rescue medication in the control group. These results indicate that failure to use cryotherapy may increase reliance on pharmacological interventions to manage postoperative discomfort, which could otherwise be mitigated through a simple and low-cost intervention such as ice pack application for 30 minutes over a 12-hour period. Therefore, the proposed cryotherapy protocol can be considered a safe and effective approach that enhances postoperative predictability, facilitates complication control, and promotes greater patient engagement in self-care.

Trismus represents a multifactorial postoperative response influenced by surgical trauma, including osteotomy, extracellular fluid extravasation, tissue hemorrhage, and muscle fiber incision. Given the simultaneous occurrence of these factors, significant benefits of cryotherapy are not expected before consolidation of the inflammatory response, which explains the absence of intergroup differences during the first 72 postoperative hours. However, when comparing immediate postoperative measurements with those obtained on postoperative day 7, the control

group exhibited significantly greater mouth opening limitation (Table 2), indicating a longer duration of trismus. This finding is supported by the statistically significant correlation between pain intensity and trismus observed exclusively in the control group (Table 3), suggesting that higher pain levels are associated with prolonged mouth opening restriction. These results were further corroborated by the quality-of-life questionnaire, which revealed greater difficulty in mouth opening among control participants.

Edema did not show statistically significant differences between groups (Table 4), consistent with previous reports. It is hypothesized that superficial ice application may be insufficient to significantly reduce edema due to its limited penetration into deeper muscular and facial tissue planes, thereby restricting its vasoconstrictive effects.

Regarding quality of life, three variables demonstrated notable percentage differences between groups. First, participants in the cryotherapy group reported less difficulty sleeping, likely reflecting the superior pain control achieved with this intervention. Second, when asked which procedure resulted in greater postoperative improvement, all 11 participants who initially underwent the control protocol reported greater improvement following the cryotherapy intervention. Participants described a reduction in burning or heat sensations and perceived a faster recovery trajectory compared with the non-cryotherapy procedure, consistent with the pain outcomes shown in Table 1. Third, patients treated with cryotherapy reported less difficulty opening their mouths, which appears to be closely related to their lower subjective pain perception. As demonstrated in Tables 1 and Graphic 2, the greater reduction in pain intensity in the test group was reflected in a lower proportion of participants reporting functional limitation.

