## 1 INTRODUCTION

Oral surgical procedures of any kind, from the extraction of a retained third molar to the rigid internal fixation of a mandibular fracture, may cause postoperative complications such as edema, trismus, and pain and interfere with the quality of life of patients. These aspects are important physiological responses but when observed at high intensity and duration, they may harm this critical period of surgical recovery.

No consensus in the literature allows defining a gold-standard protocol as postoperative conduct but most surgeons try to control the complication factors with drug therapies, from analgesics to anti-inflammatory drugs (steroidal or not). Overall, there is an underestimating of non-pharmacological maneuvers such as an effective instruction on the need for absolute rest and oral cavity hygiene, as well as cryotherapy, which is a common approach in the health field although often used empirically. The topical application of ice reduces the temperature of the skin and its adjacent tissues by 2 to 4 cm in depth, resulting in cold-induced neuropraxia and decreasing the threshold of nociceptor activation and the speed of conduction of nerve pain signals. This consequentially reduced blood flow through vasoconstriction, which may decrease the intensity of the inflammatory response of soft tissues to trauma.

The benefits of cryotherapy are not a consensus in the literature and this situation is often justified by the lack of a solid and effective treatment protocol, although the most used approach is applying ice to the region every 30 minutes in the first days. This conflict in the evidence can be seen in publications with results indicating that cryotherapy has no significant influence on edema and trismus, while other aspects report a positive increase in pain relief and other postoperative symptoms. The major unknown is still the actual influence of this therapy on pain levels.

Considering the extensive use of cryotherapy in third molar surgeries and the lack of agreement of scientific findings on its effectiveness, the present study evaluated whether the use of ice has a beneficial potential capable of reducing the intensity and duration of pain, as well as reducing edema and trismus and improve the quality of life.

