## 3 JUSTIFICATION

Cryotherapy with ice is widely used in the postoperative period as a non-pharmacological strategy for controlling these signs and symptoms, due to its potential to reduce local blood flow, inflammatory response, and nerve conduction. However, despite its routine use in clinical practice, there is still controversy in the literature regarding the actual effectiveness of ice application after third molar extraction. Therefore, it is relevant to scientifically evaluate the effects of postoperative cryotherapy following this procedure in order to support evidence-based clinical decisions and optimize postoperative recovery management.

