#### **4.6 POSTOPERATIVE CARE**

In the immediate postoperative period following the first surgical procedure, the allocation of postoperative care—with or without cryotherapy—was randomized using a simple draw. Allocation was determined by the selection of a folded paper indicating Group A or Group B and was supervised by a third party to ensure allocation concealment. When the first surgical site of a patient was assigned to Group A (control), the contralateral site in the second surgical procedure was assigned to Group B (test), and vice versa.

Group A (control) did not receive postoperative cryotherapy. Group B (test) was instructed to apply standardized ice packs (11 × 8.5 × 1 cm), provided by the research team, positioned diagonally to cover both the mandibular angle and the cheek on the operated side. Cryotherapy was initiated immediately after surgery under surgeon supervision and continued for the first 12 postoperative hours, consisting of 30-minute applications followed by 30-minute intervals (total of 12 applications). During the intervals, patients were instructed to store the ice packs in a freezer until the next application.

All participants received identical pharmacological postoperative instructions (APPENDIX B) for both interventions, including paracetamol 1 g every 6 hours for 3 days and mouth rinses with 0.12% aqueous chlorhexidine digluconate twice daily for 7 days, starting on the day following surgery. In cases of persistent pain, trismus, or edema that significantly interfered with daily activities despite the use of prescribed analgesics, patients were instructed to use rescue medication consisting of codeine 30 mg every 4 hours as needed.

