### 5 RESULTS

#### 5.1 POSTOPERATIVE PAIN INTENSITY

The analysis demonstrated significant main effects of treatment ( $F_{(1,16)} = 5.063$ ,  $p = 0.039$ ) and time ( $F_{(7,112)} = 6.254$ ,  $p < 0.001$ ) on postoperative pain intensity (Table 1). Overall, pain scores were higher in Group A than in Group B ( $2.0 \pm 1.2$  vs.  $1.3 \pm 1.1$ ;  $F_{(1,16)} = 5.063$ ,  $p = 0.039$ ).

[figure not shown]

[figure not shown]
Table 1: Average pain levels on every post-operative day for each group. (\*) indicates statistical differences between control and test groups.

In Group A, pain intensity was significantly higher on postoperative days 1 ( $3.59 \pm 0.59$ ;  $p = 0.014$ ) and 3 ( $3.24 \pm 0.55$ ;  $p = 0.005$ ) compared with day 0 ( $1.35 \pm 0.54$ ). No significant differences were observed between day 0 and the remaining postoperative time points ( $p > 0.05$ ).

[figure not shown]
On the test side (Group B), no significant differences in pain intensity were observed between day 0 and any postoperative evaluation ( $p > 0.05$ ), suggesting that cryotherapy effectively prevented postoperative pain exacerbation.

A significant interaction between treatment and time was also observed ( $F_{(7,112)} = 2.689$ ,  $p = 0.013$ ). Pain intensity was higher on postoperative day 1 (Group A:  $3.59 \pm 0.59$  vs. Group B:  $2.12 \pm 0.42$ ;  $p = 0.017$ ) and day 3 (Group A:  $3.24 \pm 0.55$  vs. Group B:  $1.29 \pm 0.33$ ;  $p = 0.007$ ) in the control group compared with the cryotherapy group.

Postoperative pain was absent in 29.4% of control cases and 44.1% of cryotherapy cases. Mild pain was reported by 50.0% of participants in Group A and 47.8% in Group B, whereas moderate pain occurred in 16.9% and 7.4% of cases, respectively. Severe pain was reported by 3.7% of control cases and 0.7% of cryotherapy cases (Graphics 1 and 2).

Graphic 1: Prevalence of reports of moderate to severe pain (4-10 in visual analogic scale) in the total number of reports of pain (1-10 in visual analogic scale) in the control group after day 2 (last day of analgesic medication).

12

Graphic 2: Prevalence of reports of moderate to severe pain (4-10 in visual analogic scale) in the total number of reports of pain (1-10 in visual analogic scale) in the test group after day 2 (last day of analgesic medication).

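### Pain was self-scored by patients who knew which side was iced, so the efficacy claims should be limited to an open-label comparison of ice with no application

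*Combined protocol and SAP*

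**What the plan says.** - **Question.** Section 1 states that "the present study evaluated whether the use of ice has a beneficial potential capable of reducing the intensity and duration of pain". Section 3 explains the routine use of ice by cooling: "due to its potential to reduce local blood flow, inflammatory response, and nerve conduction".
- **Control side.** Section 4.6: "Group A (control) did not receive postoperative cryotherapy". No substitute pack is described.
- **Ice side.** Section 4.6: "Cryotherapy was initiated immediately after surgery under surgeon supervision and continued for the first 12 postoperative hours". The packs come from the research team. After the supervised start, patients follow instructions for 12 half-hour applications and keep the packs in a freezer between them.
- **Who scores pain.** Section 4.7(a): "Patients completed the scale at home daily until postoperative day 7".
- **Masking.** The Abstract discloses that the evaluator knew the allocation. No section says whether patients did, and neither the Discussion nor the Conclusion lists this as a limitation.
- **Claims.** Section 5.1 describes the absence of a rise from day 0 on the iced side as "suggesting that cryotherapy effectively prevented postoperative pain exacerbation". Section 6 opens by calling cryotherapy effective for the intensity and duration of pain, and later credits it with synergy with the analgesics. It then says: "These findings suggest that the greater differences in pain intensity are directly associated with the absence of cryotherapy in the control group, despite the use" (the sentence ends by naming the analgesics). Section 7 repeats the efficacy claim.

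**The concern.** The person who rates the main positive outcome is the patient, and the patient cannot be unaware of the ice. Masking the evaluator would not have helped with pain, so disclosing the evaluator's awareness does not cover this outcome. Knowing which side was treated can change how much pain is felt (expectation) and how it is marked on the scale (reporting). Both would be counted in the treatment difference along with any effect of cold.

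At stake is what the trial may conclude. A reader of 5.1, 6 and 7 would take the pain result as an established effect of cryotherapy that works together with the analgesics. The design supports a narrower statement: patients who knew they were using ice reported less pain than the same patients did without it.

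**Working it through.** **Inputs**
- 17 patients, each contributing both sides (4.4).
- Pain, treatment main effect: F(1,16) = 5.063, p = 0.039; overall means 2.0 without ice and 1.3 with ice (5.1).
- Pain, treatment-by-time interaction: F(7,112) = 2.689, p = 0.013 (5.1).
- Pain by day: day 1, 3.59 vs 2.12, p = 0.017; day 3, 3.24 vs 1.29, p = 0.007 (5.1).
- Size of any expectation or reporting effect: not given.

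**1. Reproduce the printed tests.** The upper tail of F(1,16) at 5.063 is 0.0389, and that of F(7,112) at 2.689 is 0.0130. Both agree with 5.1, so the arithmetic is sound.

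**2. Size and precision of the overall difference.**
- Difference = 2.0 - 1.3 = 0.70.
- t = √5.063 = 2.250 on 16 df, so SE = 0.70 / 2.250 = 0.311.
- The critical value t(0.975, 16) is 2.120, and 2.120 × 0.311 = 0.66.
- 95% CI = 0.70 ± 0.66 = 0.04 to 1.36.
- The means are printed to one decimal, so the difference could lie between 0.6 and 0.8. The interval would then be 0.03 to 1.17 at one end and 0.05 to 1.55 at the other.

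**3. Who knew the allocation.** The evaluator did, as the Abstract states. The patient did by necessity: under 4.6 the patient applies the packs, and the second surgery gets the opposite condition to the first. The consent form is not among the pages available, but no consent wording could make an ice pack indistinguishable from nothing.

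**4. What the contrast identifies.** Let C be the effect of cold on pain and E the effect of knowing which side is iced, through expectation or reporting. The trial estimates their sum:

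C + E = 0.70

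That is one equation with two unknowns. A second would need a non-cooled pack, a masked rating or a measure of expectation, and the documents describe none of these. The data do not determine the split.

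**5. Do the other results separate C from E?**
- *Daily contrasts.* Day 1: 3.59 - 2.12 = 1.47; p = 0.017 gives t = 2.663, SE 0.552, CI 0.30 to 2.64. Day 3: 3.24 - 1.29 = 1.95; p = 0.007 gives t = 3.092, SE 0.631, CI 0.61 to 3.29. These assume paired tests on 16 df. The ratings come from the same aware patients.
- *Pain interaction.* A constant shift would leave it unchanged, so a uniform bias does not explain the day-to-day pattern. A bias that varies by day is not excluded.
- *Rescue medication and preference (5.1, 5.4).* Both depend on the patient. All 11 patients who had the control side first preferred ice, as did 83% of the rest (5 of 17 - 11 = 6). These results are not independent of awareness.
- *Mouth opening and edema.* Mouth opening has no main effect (p = 0.93) but has an interaction (p = 0.016). Edema has neither (p = 0.48 and p = 0.23). Neither measures pain, and aware staff took both measurements.

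None of these results supplies the missing equation.

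**The case against.** The strongest reply is that the trial asks a practical question. Sections 1 and 2.1 speak of using ice and of the effects of cryotherapy, and cooling appears only as background. For ice versus no ice, no application is a proper comparator, and expectation is arguably part of what ice does in practice. This stands. It does not cover differential reporting, and it does not license claims without stating that the raters were aware.

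The sentence quoted from the Discussion is also hedged. That stands too, but the opening of that section, the synergy statement, 5.1 and 7 are not hedged in the same way.

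A reader might infer several stronger points that the documents do not support:

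- *That the trial set out to test cold as such and used the wrong control.* The stated objective is broader than the mechanism.
- *That a trivial bias explains the result away, because the lower limit is 0.04.* This only restates that p = 0.039 is close to 0.05. It says nothing about how large the bias is. The interaction (p = 0.013) is untouched by a constant shift, and the daily contrasts would need shifts of about 0.30 and 0.61 points to lose significance.
- *That the larger gap on day 3, after icing ended at 12 hours, or the null edema result, argues against cold.* The Discussion identifies day 3 as the first day without the standard analgesic and offers limited penetration as a reason for the edema result. Mouth opening also shows an interaction. The pattern favours neither explanation.
- *That the ice side also had imposed rest, or supervision for the full 12 hours.* Appendix B advises rest without distinguishing the sides, and 4.6 describes supervision only at the start.
- *That the Abstract misstates comparability.* Its sentence "All intraoperative and postoperative procedures, instructions, and medications were identical for both groups" directly follows the definition of the groups by ice, and is readable in that context.

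**Conclusion.** The point holds as a limit on the claims, not as a fault in the choice of comparator. The trial gives an open-label estimate of ice-pack use against no application: 0.7 points less self-reported pain on a 0-10 scale, 95% CI 0.04 to 1.36. What share of this comes from cold, and what share from expectation or reporting, cannot be determined from these data. The unqualified efficacy wording in 5.1, 6 and 7, and the synergy claim in 6, therefore go beyond the design.

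This rests on two things. Patient awareness is inferred from the design, because no section states it. The interval is derived from the printed F statistic and rounded means. Nothing here shows that ice is ineffective or that the bias is large.

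**What to change.** 1. In the Abstract, 4.6 and 7, define the contrast as: *open-label ice-pack regimen (surgeon-supervised start, then self-applied over 12 hours) versus no application, with patients, who scored the pain, aware of allocation*.
2. In 5.1, 6 and 7, replace the unqualified pain-efficacy phrases with: *lower self-reported pain with the ice regimen than with no application, which may include expectation or reporting effects*. The hedged Discussion sentence can stay if it carries the same qualification.
3. Remove the claim of synergy with the analgesics from 6.
4. In 5.1, report the overall pain difference with its 95% CI, computed from the unrounded data. From the printed figures it is 0.7 (0.04 to 1.36).

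The cost is rewording and one interval from the existing analysis, with no new data, staff or patients. The downside is a less favourable pain conclusion.
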